11.4. Statistical Analyses

11.4.1. Populations for Analyses

The following patient populations will be defined for analysis:

- Safety Population: the Safety Population will include all randomized patients who were treated with at least one dose of IP

- Intent to Treat (ITT) Population: the ITT Population will include all randomized patients
- Modified ITT (mITT) Population: the mITT Population will include all patients aged ≥ 12 years who were randomized, received at least 1 dose of IP, had at least 1 post-randomization HQ-CT questionnaire completed, and were randomized to receive the dose level(s) recommended for development in Phase 3 of the study, including patients in the Phase 2 part of the study who received the chosen dose level(s)
- Per Protocol (PP) Population: the PP Population will include all patients aged ≥ 12 years who were randomized, received at least 1 dose of IP, completed Week 34 without significant protocol deviations that were prospectively defined to impact efficacy (see SAP) and received the dose level(s) recommended for development in Phase 3 of the study, including patients in Phase 2 of the study who received the chosen dose level(s)
- Pharmacokinetic Evaluable Population: the PK Evaluable Population will include all patients who received at least 1 dose of IP and underwent at least 1 PK sample collection.

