Following review of Phase 2 safety and tolerability data by the DMC ([Section 10.4](#)), 1 or 2 dose level(s) will be recommended for further development and assessment in Phase 3 of the study. Therefore, following the Tolerability Period, patients meeting randomization eligibility criteria will be randomized in a way to obtain a balanced number of patients on RAD011 and placebo to receive double-blind treatment with Investigational Product (IP) at dose levels recommended by the DMC. Additional details are provided in [Section 7.5](#).

Dose Escalation Period (3 weeks, Visits 5 to 7 [Weeks 7 to 9])

Phase 2 of the study

After completing the Screening and Tolerability Periods, all randomized patients will be initiated on IP (RAD011 or placebo) 10 mg/kg/day (0.1 mL/kg/day) for a period of 1 week at Visit 5 (Week 7). Patients randomized to low dose or low volume IP (10 mg/kg/day) will continue at a dose of 10 mg/kg/day (0.1 mL/kg/day) until the end of Visit 7 (Week 9). Patients randomized to mid dose or mid volume IP (20 mg/kg/day) will have their dose increased to 20 mg/kg/day (0.2 mL/kg/day) at Visit 6 (Week 8) and will continue at that dose until the end of Visit 7 (Week 9). Patients randomized to high dose or high volume IP (40 mg/kg/day) will have their dose increased to 20 mg/kg/day (0.2 mL/kg/day) at Visit 6 (Week 8) and to 40 mg/kg/day (0.4 mL/kg/day) at Visit 7 (Week 9).

Details of the dose escalation schema are provided in [Table 4](#). Patients' weight at Visit 5 (Last Tolerability Period visit / first Dose Escalation Period visit) will be used to determine the

patient's actual doses (mL/day) to be administered from Visit 5 (Week 7) through completion of the maintenance phase Visit 14 (Week 34).

The Investigator, or designee, will contact patients/caregivers by phone call, video call, email, or other remote means of communication at Visits 6 (Week 8) and 7 (Week 9) to determine if the patient's dose may be escalated to the next dose level. Dose reductions will not be allowed during the Dose Escalation Period. If a patient cannot be escalated to the next dose level, the patient will be discontinued from the study.

Phase 3 of the study

After completing the Screening and Tolerability Periods, all patients will be initiated on 10 mg/kg/day IP (0.1 mL/kg/day) for a period of 1 week at Visit 5 (Week 7).

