The 3-week Screening Period and the 6-week Tolerability Period will allow for the characterization of HQ-CT scores and help minimize potential bias in patient/caregiver completion of the HQ-CT questionnaire. These Periods will result in the exclusion of patients with too low mean scores or significant changes from Screening to the end of the Tolerability Period without any active treatment. The 6-week duration of the Tolerability Period will be sufficient to evaluate the HQ-CT scores and the tolerability of the MCT vehicle used in the RAD011 formulation. The use of inactive treatment periods in PWS studies is common as there is a recognized variability in hyperphagia behavior and HQ-CT response behaviors.

Once randomized, patients will enter the 3-week Dose Escalation Period followed by a 24-week Maintenance Period. This combined 26-week treatment period was designed to allow for potential placebo effect to wane and allow for the evaluation of separation of effects between placebo and RAD011 groups.

The target population for this study has also been carefully selected to include patients with moderate to severe hyperphagia (HQ-CT scores ≥ 13) ([Fehnel, 2015](#)). This is in line with baseline severity in other PWS development programs. In terms of age, the primary efficacy analysis will be based on the modified ITT (mITT) population ([Section 11.4.1](#)) which comprises patients aged 12 to 65 years. However, as the median age of transition into Phase 3 hyperphagia is 8 years (interquartile range of 5 to 13 years), patients aged 8 to < 12 years may also benefit from efficacious hyperphagia management ([Miller, 2011](#)). However, since a significant proportion of patients below the age of 12 years may not have established hyperphagia because developmental milestones may significantly affect food-seeking behaviors and environmental interactions, and

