5.7.1. Dose Level (mg/kg/day) Reduction for Tolerability During the Dose Escalation Period

Dose reductions for tolerability are not allowed during the Dose Escalation Period. Patients unable to tolerate their assigned dose level(s) during the Dose Escalation Period will be withdrawn from the study.

5.7.2. Dose Level (mg/kg/day) Reduction for Tolerability During the Maintenance Period (Weeks 10 to 34)

In the event that a patient does not tolerate their assigned dose level on a mg/kg/day basis during the Maintenance Period, the Investigator may decrease the patient's dose by 25% at any time during the Maintenance Period after consultation with the Sponsor as detailed in [Table 5](#). Patients undergoing a dose reduction may not have their dose increased back to their originally assigned dose. If a second dose reduction is required for tolerability during the Maintenance Period, the patient should be discontinued from the study in consultation with the Sponsor.

Table 5: Dose Level (mg/kg/day) Reduction for Tolerability during the Maintenance Period

Dose Prior to Performing Dose Reduction	Dose Following Dose Reduction (25% Decrease)
10 mg/kg/day 0.1 mL/kg/day	7.5 mg/kg/day 0.075 mL/kg/day
20 mg/kg/day 0.2 mL/kg/day	15 mg/kg/day 0.15 mL/kg/day
40 mg/kg/day 0.4 mL/kg/day	30 mg/kg/day 0.3 mL/kg/day

Reasons for dose reduction due to tolerability may include, but are not limited to, diarrhea, somnolence, lethargy, hepatotoxicity, insomnia, psychomotor hyperactivity, aggression, anemia, and ataxia.

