5.8.4.2 Visits 6 and 7 (Weeks 8 and 9)

The following assessments must be performed (remotely or in person) during Visits 6 and 7 (Weeks 8 and 9):

- Review of concomitant medications
- Review of AEs
- Food Diary Reminder and Food Diary Distribution (Visit 7 only): patients will be instructed to record the time of their evening and morning doses of study medication on the night prior to and the day of their next clinic visit with the type of meal administered.

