5.8.5.1 Visits 8, 10, 12, and 14 (Weeks 10, 19, 27, and 34)

The following assessments must be performed in person during Visits 8, 10, 12, and 14 (Weeks 10, 19, 27, and 34):

- Review of concomitant medications
- Review of AEs
- Weight and height
- Vital signs, including BP, HR, temperature, RR, and oxygen saturation
- Abbreviated, symptom-directed physical examination
- Completion of the HQ-CT, C-SSRS, CGI-S Hyperphagia, CaGI-S Hyperphagia and ABC questionnaires
 - The same caregiver should be available throughout the study to complete the questionnaires with the patients
- Visits 10 and 14 only: completion of the ESS-CHAD and Skin Picking questionnaires
- Resting 12-lead ECG in the supine position (except Visit 12)
- Collection of laboratory samples ([Section 10.1](#))
 - Urinalysis
 - Urine dipstick pregnancy test for females of childbearing potential only, to be performed locally
 - Chemistry panels (renal and liver function panels)

- Hematology
- Glycosylated hemoglobin at Visits 8, 12, and 14 only
- Appetite hormones (including insulin, ghrelin, and leptin). Ghrelin samples will only be collected for Phase 3 patients at sites where proper collection is feasible. To be collected at Visits 8, 12, and 14 only
- Pharmacokinetic sample at Visits 8, 12, and 14 only ([Section 10.1.13](#))
 - Blood draws for PK analyses of CBD, 7-OH-CBD, and 7-COOH-CBD will be drawn at the same time as the other laboratory samples. The time of sampling will be recorded, with the exception of Visit 8 (Week 10). Pharmacokinetic sampling on Visit 8 should occur within 6 ± 2 hours of dose. The food diary completed prior to each Visit 8, 12, and 14 will be collected prior to the blood draw.
- Food diary collection (Visits 8, 12, and 14 only): patients will have been instructed to record the time of their evening and morning doses of study medication on the night prior to and the day of their Visits 8, 12, and 14, with the type of meal administered
- Drug accountability
- Dispensing of IP (at Visit 14, only dispense if the patient proceeds to the Taper Period)
- Visit 14 only: completion of the CGI-C Hyperphagia, CaGI-C Irritability, and CaGI-C questionnaires, and patient's impression of seizures
- Visit 14 only: Biomarker samples. Biomarker assessments will only be performed in patients enrolled in the Phase 3 part of the study and be optional. Biomarker assessments will not be conducted in the Phase 2 part of the study)

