ⁱ Chemistry panels include renal and liver function panels. Renal function panel includes sodium, potassium, chloride, calcium, bicarbonate, glucose, phosphorus, blood urea nitrogen, creatinine, and estimated glomerular filtration rate. Should be obtained after a 10-hour fast if possible. Liver function panel includes ALT, AST, albumin, alkaline phosphatase, direct bilirubin, total bilirubin, indirect bilirubin, and total protein (Table 9).

^j Hematology panel includes hematocrit, hemoglobin, MCV, MCH, MCHC, RDW, RBC, WBC, platelets, and differential (Table 9).

^k FSH levels must be ≥ 30 mIU/mL with absence of menstruation for ≥ 1 year to be considered menopausal status ([Section 10.1.11](#)).

^l Includes insulin, ghrelin, and leptin ([Table 9](#)). Ghrelin samples will only be collected for Phase 3 patients at sites where proper collection is feasible.

^m Will only be performed in patients enrolled in the Phase 3 part of the study and be optional. Biomarker assessments will not be conducted in the Phase 2 part of the study.

ⁿ Review of eligibility at Visit 1 includes all inclusion and exclusion criteria with the exception of HQ-CT. Eligibility related to HQ-CT scores will be assessed at Visit 2 and Visit 5 ([Section 6.4](#)).

^o Dosing should be completed at the site when patients are present for a study visit during Visit 2 and Visit 5 ([Section 7.1](#))

^p Patients will be instructed to record the time of their evening and morning doses of study medication on the night prior to and the day of their next clinic visit with the type of meal administered. Patients should also be contacted approximately 1 week prior to their next visit to remind them to complete their food diary prior to their next visit ([Section 10.1.14](#)).

Table 7: Schedule of Assessments – Dose Escalation, Maintenance, Taper, and Follow-Up Periods

Period	DOUBLE-BLIND TREATMENT PHASE ^a										TAPER PERIOD ^b (2 weeks)	FOLLOW-UP PERIOD ^b (2 weeks)	
	DOSE ESCALATION PERIOD ^a (3 Weeks)			MAINTENANCE PERIOD (24 Weeks)									
Visit Number	5 ^{c,d}	6 ^e	7 ^{e,f}	8 ^c	9 ^e	10 ^c	11 ^{e,f}	12 ^c	13 ^{e,f}	14 ^{c,g,aa,bb}	15 ^c	16 ^e	
Study Time Point	D 43 (W 7)	D 50 (W 8) (Remote)	D 57 (W 9) (Remote)	D 64 (W 10)	D 99 (W 15) (Remote)	D 127 (W 19)	D 155 (W 23) (Remote)	D 183 (W 27)	D 204 (W 30) (Remote)	D 232 / ET/EOS (W 34)	D 232 (W 34)	D 246 ^c (W 36 ^c) (Remote)	D 260 ^e / EOS ^e (W 38) (Remote)
Visit Window (D)	±3	±3	±3	±3	±3	±3	±3	±3	±3	±3	±3	±3	±3

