11.4.2. Primary Endpoint

The primary endpoint, change in HQCT score from Baseline to End of Study (Week 34) will be analyzed for the mITT population based on the treatment policy estimand using a mixed model for repeated measures (MMRM) with change in HQCT score as the response variable and randomization assignment, Baseline HQ-CT score and stratification variables (age [≥ 16 or < 16 years] at randomization and GH treatment at randomization [yes/no]) and time \times treatment interaction as fixed effects. Patient will be included as a random effect with an unstructured covariance matrix. A multiple imputation will be used for missing data. Baseline will be defined as the mean HQ-CT score (Visit 1, Visit 2).

For the primary endpoint analysis at Week 34, multiple imputation will be used to assign a value to those cases with missing data. The full conditional specification method with predictive means matching as described in Berglund & Heeringa ([Berglund, 2014](#)) will be used. This method uses all of a patient's known primary outcome measures at Baseline, Weeks 10, 19, 27, and/or 34 weeks to impute any missing values for Week 34.

DMC Recommendation of two RAD011 Doses

The primary comparison will be mean change in HQ-CT as calculated via least square means comparing RAD011 low dose vs. placebo and RAD011 high dose vs. placebo at Week 34. Low dose and high dose groups will be compared to placebo at the two-sided 0.025 level so overall type 1 error is maintained at two-sided 0.05 level.

DMC Recommendation of one RAD011 Dose

The primary comparison will be mean change in HQ-CT as calculated via least square means comparing RAD011 vs. placebo at Week 34. RAD011 will be compared to placebo at the two-sided 0.05 level.

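### Patients who fail dose escalation are withdrawn from the study, which can end HQ-CT collection before its first scheduled post-randomisation assessment, although the treatment-policy estimand needs their Week 34 score

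*Protocol*

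**What the plan says.** **Estimand and analysis set.** Section 11.4.2 says that the primary endpoint "will be analyzed for the mITT population based on the treatment policy estimand using a mixed model for repeated measures (MMRM" (the abbreviation closes the phrase). Section 5.2 agrees that "the primary efficacy analysis will be based on the modified ITT (mITT) population". Under Section 11.4.1, mITT covers randomised patients aged 12 or over, assigned to the dose level(s) taken into Phase 3, who "received at least 1 dose of IP, had at least 1 post-randomization HQ-CT questionnaire completed".

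**Escalation failure.** Section 5.1 states: "If a patient cannot be escalated to the next dose level, the patient will be discontinued from the study". Section 5.7.1 states: "Patients unable to tolerate their assigned dose level(s) during the Dose Escalation Period will be withdrawn from the study". The Synopsis and Section 6.3.3 carry the same rule. All four refer to the study, not only to IP.

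**Stopping IP in general.** Section 6.3.1 says that patients who stop IP without withdrawing consent or assent stay on the planned assessment schedule, without drug dispensing or accountability. Those unwilling or unable to do so should have the End of Study (Visit 14) assessments.

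**HQ-CT schedule.** Section 5.8.4.2 introduces the escalation contacts with "The following assessments must be performed (remotely or in person) during Visits 6 and 7 (Weeks 8 and 9" and lists concomitant medication, adverse events and the food diary, but no HQ-CT. Section 5.8.5.1 introduces the maintenance visits with "The following assessments must be performed in person during Visits 8, 10, 12, and 14 (Weeks 10, 19, 27, and 34" and does list the HQ-CT. Table 7 labels Visit 14 "D 232 / ET/EOS (W 34", so it also serves as the early-termination visit.

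**The concern.** A treatment-policy estimand uses the outcome at Week 34 whether or not the patient is still on treatment. That requires the outcome to be collected after treatment stops. Section 6.3.1 provides for this, but the escalation wording can be read as ending participation altogether, in the weeks when intolerance is most likely to lead to removal.

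A condition of at least one post-baseline value often does little harm. Here the first scheduled value falls after the whole escalation period, so membership of the primary set can depend on tolerating escalation, which treatment can affect. If failures are more frequent on active drug and do worse than those who remain, the comparison is no longer the randomised one and leans towards the drug. An SAP can redefine a set or an imputation model, but it cannot recover Week 34 scores that were never collected.

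**Working it through.** **1. Schedule (Sections 5.8.4.1, 5.8.4.2 and 5.8.5.1; Table 7).**
- Visit 5, Day 43: HQ-CT completed before randomisation, so it does not count as post-randomisation.
- Visits 6 and 7, Days 50 and 57: no HQ-CT.
- Visit 8, Day 64: first scheduled post-randomisation HQ-CT, 64 − 43 = 21 days after randomisation.

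A patient withdrawn for intolerance before Day 64 has no scheduled post-randomisation score. Without an early-termination HQ-CT, that patient is outside mITT, and imputation within mITT cannot bring the patient back.

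**2. The rules side by side.** The Synopsis and Sections 5.1, 5.7.1 and 6.3.3 remove the escalation-intolerant patient from the study. Section 6.3.1 continues follow-up after IP stops, and Section 5.4 says that anyone who has had a dose will be in the analyses. Nothing says which governs outcome collection in this patient.

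**3. The plan's own figures (Section 11.1).** Difference 5, SD 7, 50 per group: noncentral-t power is 0.900 at two-sided 0.025 (stated 90%) and 0.943 at 0.05 (stated 94%). Allowing for dropout, 50 / (1 − 0.15) = 58.8, or 59 per group. These reproduce. The inputs 5, 7 and 59 are used below.

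**4. Size at the assumed extreme.** Let f be the share of an active arm that fails escalation and is excluded. The protocol gives no value. I take 3% to 15%, the top being the whole dropout allowance. Assume no exclusions on placebo, no benefit in those lost, and 5 points in the rest. Then mITT estimates 5, the treatment-policy difference is 5 × (1 − f), and the overstatement is 5f.

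| f | Excluded of 59 | Treatment-policy difference | Overstatement |
|---|---|---|---|
| 3% | 1.8 | 4.85 | 0.15 |
| 10% | 5.9 | 4.50 | 0.50 |
| 15% | 8.85 | 4.25 | 0.75 |

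**5. Placebo patients also fail.** With the same 5-point shortfall in both arms, the overstatement is 5 × (active rate − placebo rate). For 10% against 5% it is 0.25; at equal rates it is zero.

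**6. Some failures give an early-termination HQ-CT.** If half do, and their Week 34 value is correctly imputed as no benefit, mITT estimates 5(1 − f)/(1 − f/2) = 4.92, 4.74 and 4.59. The overstatement falls to 0.07, 0.24 and 0.34.

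**7. Does redefining the set cure it?** Section 11.4.2 imputes from the patient's own HQ-CT scores, so a patient with no later score is imputed from Baseline alone. I simulated 59 per arm, 4,000 runs, with predictive mean matching within arm on Baseline (within arm is my assumption; the protocol does not say).

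| f | mITT | All randomised, imputed | True treatment-policy value |
|---|---|---|---|
| 3% | 4.98 | 4.98 | 4.83 |
| 10% | 5.00 | 4.99 | 4.50 |
| 15% | 5.01 | 5.01 | 4.27 |

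The imputed values are borrowed from patients who stayed on treatment, so the wider set reproduces the mITT answer.

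**The case against.** **Exclusion is not automatic.** Section 6.3.1 sends patients who stop IP and will not follow the schedule to the Visit 14 assessments, which include the HQ-CT. Section 6.3.3 encourages the same on withdrawal of consent, and one such score satisfies the mITT condition. This stands: a reader might infer that escalation failures are certainly lost from the primary set, and the text does not support that. Still, no section expressly requires the assessment when the investigator withdraws a patient for escalation intolerance, and a score taken at early termination is not a Week 34 outcome.

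**Loss of Week 34 data is not certain.** Section 6.3.3 ends all procedures and follow-up expressly only on withdrawal of consent or assent, and Section 7.2.1 lets a patient stop treatment and stay on study after drug-interaction events. This also stands. A missing Week 34 score is the likely reading of conflicting sections, not a stated rule.

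**The size rests on an extreme.** Placebo is volume-matched in the same vehicle and escalates identically, and Section 5.6 describes earlier experience up to the highest dose as generally well tolerated. So the figures are upper illustrations, not forecasts.

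**ITT is also analysed.** Section 11 plans it, but it is not primary and includes ages 8 to under 12. No planned set is all randomised patients aged 12 or over on the selected dose(s) or placebo.

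**The one-dose condition is not the problem.** Agreed: the mechanism concerns dosed patients.

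**Conclusion.** The protocol contradicts itself on follow-up after escalation failure, and one side of the contradiction defeats the estimand it names. This should be fixed. The overstatement is 0.15 to 0.75 points on a 5-point difference if 3% to 15% of an active arm is lost, none on placebo, and those lost gain nothing. It shrinks with early-termination scores or placebo failures with a similar shortfall, and is zero at equal rates with equal shortfall. The failure rates are assumptions.

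Two stronger conclusions should not be drawn. First, the mITT wording alone is not the operative defect, because step 7 shows that widening the set without new data changes nothing. Secondly, a reader might infer that power falls well below the stated 90% by applying the diluted differences to 50 per group. That counts dropout twice. With all 59 per group analysed at two-sided 0.025, power at 4.85, 4.50 and 4.25 is about 93%, 89% and 85%.

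**What to change.** **Main change.** Reconcile the Synopsis and Sections 5.1, 5.7.1 and 6.3.3 with Section 6.3.1, so that patients who stop IP during escalation and keep consent continue HQ-CT collection at Weeks 10, 19, 27 and 34. This concerns outcome collection only; no dose or stopping rule is proposed.

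**Secondary change.** Remove the post-randomisation HQ-CT condition, so that the primary set is randomised patients aged 12 or over assigned to the selected dose(s) or placebo. Keep the present mITT as a sensitivity set. For patients who still have no off-treatment data, do not rely on within-arm imputation from Baseline alone. Use a method that reflects treatment discontinuation, such as retrieved-dropout or placebo-based imputation.

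**Cost.** Protocol wording, up to four HQ-CTs in a few off-treatment patients, and possibly a slightly smaller estimated effect.

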11.4.2. Primary Endpoint

The primary endpoint, change in HQCT score from Baseline to End of Study (Week 34) will be analyzed for the mITT population based on the treatment policy estimand using a mixed model for repeated measures (MMRM) with change in HQCT score as the response variable and randomization assignment, Baseline HQ-CT score and stratification variables (age [≥ 16 or < 16 years] at randomization and GH treatment at randomization [yes/no]) and time \times treatment interaction as fixed effects. Patient will be included as a random effect with an unstructured covariance matrix. A multiple imputation will be used for missing data. Baseline will be defined as the mean HQ-CT score (Visit 1, Visit 2).

For the primary endpoint analysis at Week 34, multiple imputation will be used to assign a value to those cases with missing data. The full conditional specification method with predictive means matching as described in Berglund & Heeringa ([Berglund, 2014](#)) will be used. This method uses all of a patient's known primary outcome measures at Baseline, Weeks 10, 19, 27, and/or 34 weeks to impute any missing values for Week 34.

DMC Recommendation of two RAD011 Doses

The primary comparison will be mean change in HQ-CT as calculated via least square means comparing RAD011 low dose vs. placebo and RAD011 high dose vs. placebo at Week 34. Low dose and high dose groups will be compared to placebo at the two-sided 0.025 level so overall type 1 error is maintained at two-sided 0.05 level.

DMC Recommendation of one RAD011 Dose

The primary comparison will be mean change in HQ-CT as calculated via least square means comparing RAD011 vs. placebo at Week 34. RAD011 will be compared to placebo at the two-sided 0.05 level.

